**Table 3 – ISS staging definition**

Stage	Definition
Stage I	Serum $\beta$ 2-microglobulin <3.5 mg/L and serum albumin $\geq$ 35 g/L
Stage II	serum $\beta$ 2-microglobulin <3.5 mg/L and serum albumin <35 g/L or serum $\beta$ 2-microglobulin 3.5 - <5.5 mg/L regardless of serum albumin levels
Stage III	Serum $\beta$ 2-microglobulin $\geq$ 5.5 mg/L regardless of serum albumin levels

**Table 4 – Derivation of measurable paraprotein at study entry**

Measurable paraprotein	Criteria
Serum M-Protein	Serum M-Protein $\geq$ 0.5 g/dL and urine M-Protein < 200 mg/24hours or missing
Urine M-Protein	Serum M-Protein < 0.5 g/dL or missing and urine M-Protein $\geq$ 200 mg/24hours
Serum M-Protein and Urine M-Protein	Serum M-Protein $\geq$ 0.5 g/dL and urine M-Protein $\geq$ 200 mg/24hours

### ***Molecular subtype at initial diagnosis***

Molecular subtype included cytogenetics analysis by FISH (as collected in the e-CRF).

### ***Molecular subtype at study entry***

Molecular subtype included cytogenetics analysis by FISH which are 17p deletion, t (4, 14), and t (14; 16). High risk group is defined as patients with at least one chromosomal abnormality.

### ***Prior anticancer therapies***

- Prior anticancer treatments: number of prior lines (2, 3, 4, 5, 6, 7 and  $\geq$  8 and as a quantitative variable), main category of drug (i.e., alkylating agent, anthracycline, proteasome inhibitor, immunomodulatory drugs others), drug name (i.e., melphalan, cyclophosphamide, doxorubicin, lenalidomide, pomalidomide, thalidomide, bortezomib, carfilzomib, ixazomib, elotuzumab, and panobinostat), time from completion of last line of treatment to first Investigational Medicinal Product (IMP) administration (months), best response to last line, duration of last line of therapy.

In addition, the refractory status to each anticancer treatment will be derived. A patient is considered to be refractory if any of the following conditions are met:

- Progression date and anticancer treatment end date are complete and progression date is within ( $\leq$ ) 60 days of anticancer treatment end date (progression date – anticancer treatment end date  $\leq$  60 days). If only the day is missing for either date or both dates, and the progression date and anticancer treatment end date corresponds to two consecutive months within the same year, then, the patient will be considered refractory, otherwise they will be considered not refractory.
- Best overall response is SD or PD.
- Reason for treatment discontinuation is “disease progression”
- Prior transplant: number (%) of patients with transplant, number (%) of transplant by patient (1, 2 and  $\geq$ 3)
- Prior surgery: number (%) of patients with any prior surgery and time from last surgery to first IMP administration (months)
- Prior radiotherapy: number (%) of patients with any prior radiotherapy, intent (curative and palliative), type (systemic, internal beam, and external beam), and time from last radiotherapy to first IMP administration (months)

Any technical details related to computation, dates, and imputation for missing dates, are described in [Section 2.5](#).

### **2.1.2 Prior or concomitant medications (other than anticancer therapies)**

All medications taken within 7 days prior to first dose of IMP, at any time during the treatment period, and up to 30 days after the last isatuximab administration are reported in the e-CRF.

All medications will be coded using the World Health Organization-Drug Dictionary (WHO-DD) version in effect at Sanofi (or the data management vendor) at the time of the data base lock.

- Prior medications are those the patient used prior to first isatuximab administration. Prior medications can be discontinued before first administration or can be ongoing during treatment phase.
- Concomitant medications are any treatments received by the patient concomitantly to isatuximab, from first dose to the date of last administration + 30 days. A given medication can be classified both as a prior medication and as a concomitant medication.  
Concomitant medications do not include medications started during the post treatment period (as defined in the observation period in [Section 2.1.4](#)).
- Post treatment medications (excluding post anticancer treatments) are those the patient took from 31 days after last isatuximab administration up to the end of the study.

### ***Pre-medication***

Patients are to routinely receive pre-medications prior to isatuximab infusion to reduce the incidence and severity of hypersensitivity reactions. Pre-medications were defined in the protocol as non-IMP(s). The recommended pre-medication agents were: diphenhydramine 25-50 mg IV (or equivalent), methylprednisolone 100 mg IV (or equivalent), ranitidine 50 mg IV (or equivalent), and acetaminophen 650-1000 mg po 15-30 minutes (but no longer than 60 minutes) prior to isatuximab infusion. Analysis of pre-medications will focus on antihistamine, corticosteroids, h2 blocker, and acetaminophen given (start and stop dates) on the days of isatuximab administrations.

Any technical details related to computation, dates, imputation for missing dates are described in [Section 2.5](#).

#### **2.1.3 Efficacy endpoints**

All efficacy endpoints are defined as secondary objectives.

Disease assessments are performed every cycle by the Independent Adjudication Committee (IAC) using the IMWG criteria. The assessment of “Progressive disease” by the site doctor (collected in e-CRF) will not be used for phase 1 in efficacy analysis.

The following efficacy endpoints will be derived for the phase 1 part of the study.

Best overall response (BOR): defined as the best sequential response in every cycle’s assessment from the start of treatment through the entire study excluding any time point following the start of other treatment for MM. The ordering of evaluations from best to worse is: stringent complete response (sCR), complete response (CR), very good partial response (VGPR), partial response (PR), minimal response (MR), stable disease (SD), progressive disease (PD), not evaluable (NE). Confirmation of response is needed.

Overall survival (OS): defined as the time interval from the date of first study treatment administration to death due to any cause. In the absence of the confirmation of death before the analysis cutoff date, OS will be censored at the last date the patient is known to be alive or at the study cutoff date, whichever is earlier.

Progression free survival (PFS): defined as the time interval from the date of first study treatment administration to the date of the first assessed disease progression or death due to any cause, whichever comes first. In the absence of disease progression, death before the analysis cutoff date or death before the date of initiation of new anticancer treatment, PFS will be censored at the earliest of the date of the last valid assessment not showing disease progression performed before initiation of new anticancer treatment or the analysis cutoff date, whichever is earlier.

Duration of response (DOR): DOR is defined as the time from first response that is subsequently confirmed to the first documented tumor progression or death. If progression or death is not observed, the date of the last valid disease assessment performed before cutoff date or initiation of

a new anticancer treatment will be used. DOR is determined only for patients who have achieved a response of  $\geq$  PR and will not be calculated for patients who did not achieve a response.

Time to response (TTR): TTR is defined as the time from first dose to first response (PR or better) that is subsequently confirmed.

#### **2.1.4 Safety endpoints**

The safety analysis will be based on the reported adverse events and other safety information, such as clinical laboratory data, vital signs, ECG, etc.

##### *Observation period*

The observation period will be divided into 3 periods: pre-treatment, on-treatment and post-treatment.

- The **pre-treatment period** is defined as the time from when the patients give informed consent and the start of isatuximab.
- The **on-treatment period** is defined as the time from first dose of isatuximab up to 30 days after the last dose of isatuximab.
- The **post-treatment period** is defined as the time from 31 days after the last dose of isatuximab to the study closure.

##### **2.1.4.1 Adverse events variables**

All adverse events occurring from informed consent signature until at least 30 days after the last isatuximab administration and new adverse events related to isatuximab on the post-treatment period will be collected in the e-CRF. The severity of AEs will be assessed according to NCI-CTCAE version 4.03.

All adverse events (including serious adverse events [SAEs]) will be coded to a lower-level term (LLT), preferred term (PT), high-level term (HLT), high-level group term (HLGT), and associated primary system organ class (SOC) using the version of Medical Dictionary for Regulatory Activities (MedDRA) in effect at Sanofi (or the data management vendor) at the time of the data base lock.

##### *Adverse event observation period*

- Pretreatment adverse events are adverse events that developed or worsened or became serious during the pre-treatment period.
- Treatment-emergent adverse events are adverse events that developed or worsened or became serious during the on-treatment period.
- Post-treatment adverse events are adverse events that developed or worsened or became serious during the post-treatment period.

### ***Adverse events of special interest***

The following AEs are considered adverse events of special interest (AESIs):

- Acute infusion associated reactions (IARs)
- DLTs
- Symptomatic overdose
- Pregnancy occurring in a female patient or in a female partner of a male patient

### ***Infusion associated reactions***

Infusion associated reactions, commonly observed with monoclonal antibodies, include AEs with onset date typically within 24 hours from the start of each isatuximab infusion (See Section 6.6 of the protocol for guidelines for IARs management). As described above, IARs are considered to be AESI.

Two analyses of IARs will be performed. The first one will be based on the investigator's reporting of IARs (i.e., as AESIs). For each IAR-AESI, the sites were instructed to report a generic term (infusion related reaction) and each individual symptom. For IAR analyses based on the generic term, a customized MedDRA query (CMQ) including the single preferred term of infusion related reaction will be used.

The second analysis of IAR will include TEAEs occurring within 24 hours (one table including causally related TEAEs, one table including all TEAEs regardless of causal relationship) from the start of each isatuximab infusion (i.e., TEAEs with onset on the same calendar day of the isatuximab infusion or on the following day).

### ***Respiratory AEs***

Analysis of respiratory TEAEs will focus particularly on the groupings by CMQ.

### ***Hematological analyses***

Neutropenic complications will focus particular on the groupings by CMQ.

#### **2.1.4.2 Deaths**

The deaths observation period are based on the observation periods defined in [Section 2.1.4](#).

- Death on-treatment: deaths occurring during the on-treatment period
- Death post-treatment: deaths occurring during the post-treatment period

#### **2.1.4.3 Laboratory safety variables**

Clinical laboratory data consists of blood analysis, including hematology, clinical chemistry, and urinalysis. Clinical laboratory values will be converted into standard international units and international units that will be used in all listings and tables.

Blood samples for clinical laboratories will be taken as defined in the study flow charts and as clinically indicated. The laboratory parameters will be classified as follows:

- Hematology
  - **Red blood cells and platelets and coagulation:** hemoglobin, hematocrit, mean corpuscular volume, red blood cell count, platelet count, prothrombin time (expressed as international normalized ratio), activated partial thromboplastin time
  - **White blood cells:** white blood cell count, neutrophils, lymphocytes, monocytes, basophils, eosinophils
- Clinical chemistry
  - **Metabolism:** glucose, total protein, albumin
  - **Electrolytes:** sodium, potassium, chloride, calcium, corrected serum calcium, phosphate, magnesium
  - **Renal function:** creatinine, blood urea nitrogen, uric acid, e-GFR (revised equations for e-GFR in Japanese)
  - **Liver function:** alanine aminotransferase, aspartate aminotransferase, alkaline phosphatase, lactate dehydrogenase, total and conjugated (direct) bilirubin
  - **Pregnancy test:** serum  $\beta$ -human chorionic gonadotropin (all female patients)
  - **Hepatitis screen:** hepatitis B surface antigen (HBs-Ag, HBc-Ab, and HBs-Ab), HBV-DNA, anti-hepatitis-C antibody (HCV-Ab)

Urine samples will be collected as follows:

- **Urinalysis** – quantitative: pH, leukocytes, erythrocytes and specific gravity
- **Urinalysis** – qualitative: blood, ketones, bilirubin, leucocytes, nitrates, proteins and glucose

#### **2.1.4.4 Vital signs variables**

Vital signs include: heart rate, respiratory rate, temperature, body weight, and systolic/diastolic blood pressure.

#### **2.1.4.5 Electrocardiogram variables**

Electrocardiogram variable include: 12 leads electrocardiogram and 2-D echocardiogram or MUGA scan.

#### **2.1.4.6 Other safety endpoints**

Other safety endpoints include:

- Cytokines
  - TNF- $\alpha$ , IL-4, IL-6, IL-1- $\beta$ , IFN- $\gamma$
- IAR laboratory test
  - Complement (C3a, C4, CH50)
  - Serum tryptase
- Chest X-ray at baseline and as clinically indicated
- Tumor lysis syndrome (TLS)

#### **2.1.5 Pharmacokinetic variables**

The PK sampling times were provided in the study flowcharts.

Isatuximab concentrations will be analyzed with the PKDMS software (Pharsight) using non-compartmental methods for all cohorts. The following PK parameters will be calculated following the first administration:

- Concentration observed at the end of an IV infusion ( $C_{eoi}$ )
- Maximum observed concentration ( $C_{max}$ )
- Time to reach  $C_{max}$  ( $t_{max}$ )
- Concentrations just before drug infusion ( $C_{trough}$ )
- AUC over the dosing interval ( $AUC_{1\text{week}}$ )

$C_{trough}$  are defined as sample collected before dosing of all cycles, and in a time window of 6 to 8 days after the previous start of infusion for the QW administration.

#### **2.1.6 CD38 Receptor density**

CD38 RD will be assessed from bone marrow aspirates at baseline.

#### **2.1.7 Immune response**

Human ADA status to isatuximab was assessed during the study as defined in the protocol.

##### ***Observation period***

The observation period will be divided into 2 periods: ADA pre-treatment and ADA on-study observation.

- ADA pre-treatment period: The ADA pre-treatment period is defined as the time from signed informed consent to the first isatuximab administration.

- ADA on-study observation period: the ADA on-study observation period is defined as the time from first isatuximab administration until Cycle 10.

Patients with at least one ADA result during the ADA on-study observation period will be considered evaluable for ADA.

***ADA attributes:***

- Pre-existing ADA is defined as ADA that was present in samples drawn during the ADA pretreatment period.
- Treatment boosted ADA is defined as preexisting ADA with an increase in titer value between pre-treatment and post-treatment samples of at least two titer steps during the ADA on-study observation period. With a 2-fold serial dilution, this means that the posttreatment sample titer value is at least ( $\geq$ ) 4 fold of pretreatment titer value.
- Treatment-induced ADA is defined as ADA that developed at any time during the ADA on-study observation period in patients without pre-existing ADA, including patients without pretreatment samples.
- Transient ADA response is defined by:
  - Treatment induced ADA detected only at one sampling time point during the ADA on study observation period (excluding the last sampling time point), OR
  - Treatment induced ADA detected at two or more sampling time points during ADA on-study observation period, where the first and last ADA-positive samples (irrespective of any negative samples in between) are separated by a period less than 16 weeks, and the patient's last sampling time point is ADA negative.
- A persistent ADA response is defined by:
  - Treatment induced ADA detected at two or more sampling time points during the ADA on-study observation period, where the first and last ADA-positive on study samples are separated by at least 16 weeks (irrespective of any negative samples in between), OR
- Indeterminate ADA response is defined by:
  - Treatment induced ADA detected only at the last sampling time point with all previous samples being negative, OR
  - The last two samples being ADA-positive and separated by a period of less than 16 weeks.

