25. ADA (Anti-Drug Antibodies): To be performed on Day 1, Day 8, Day 15, Day 22 of Cycle 1 and Day 1 of cycle up to 10 cycles prior to each IMP administration, at the EoT visit and at 60 days (\pm 7 days) after last IMP administration. At 60 days, if patient is positive for ADA or the sample is inconclusive, additional ADA samples are required every 30 days (\pm 7 days) until sample is negative. If ADA is positive at Cycle 10, one additional sampling for ADA evaluation should be collected 3 months later. No further ADA will be collected, even if the 3-month sample is positive.

26. Peripheral blood to be collected on Day 1 of Cycle 1 prior to IMP administration for soluble CD38 analysis.
27. Bone Marrow Aspiration and/or biopsy: Bone marrow aspiration (BMA) to be collected at screening/baseline. In case of dry-tap, bone marrow biopsy to be performed. Repeat bone marrow aspiration and/or biopsy if complete response (CR) is suspected to confirm achievement of response.
28. MRD Assessment: Bone marrow aspiration and/or biopsy to be collected at screening/baseline. Repeat bone marrow aspiration and/or biopsy if CR is suspected.
29. CD38 Receptor Density in bone marrow: Bone marrow aspiration to be performed prior to study drug administration at screening/baseline. See PK flowchart.
30. Cytogenetics/ FISH: Bone marrow aspiration and/or biopsy to be performed prior to study drug administration at screening/ baseline for fluorescence in situ hybridization (FISH) analysis. Probes include those to detect del(17p), t(4;14) and t(14;16).
31. Immune phenotyping (BM): Bone marrow aspiration and/or biopsy to be performed at baseline/screening prior to IMP administration.
32. Immune phenotyping (peripheral blood): To be performed at Day 1 of Cycle 1, Day 1 of Cycle 3 prior to IMP administration and at the EoT visit. Immune phenotyping in bone marrow will be performed by bone marrow sample obtained at the screening/ baseline period.
33. Immune genetic determinants (peripheral blood): includes Killer cell Ig-like receptors (KIR), HLA Typing and Fc γ R genes. To be performed at Day 1 of Cycle 1 prior to IMP administration.

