***ADA attributes:***

- **Pre-existing ADA** is defined as ADA that was present in samples drawn during the ADA pretreatment period.
- **Treatment boosted ADA** is defined as preexisting ADA with an increase in titer value between pre-treatment and post-treatment samples of at least two titer steps during the ADA on-study observation period. With a 2-fold serial dilution, this means that the post-treatment sample titer value is at least ( $\geq$ ) 4 fold of pretreatment titer value.
- **Treatment-induced ADA** is defined as ADA that developed at any time during the ADA on-study observation period in patients without pre-existing ADA, including patients without pretreatment samples.
- **Transient ADA response** is defined by:
  - Treatment induced ADA detected only at one sampling time point during the ADA on study observation period (excluding the last sampling time point), OR
  - Treatment induced ADA detected at two or more sampling time points during ADA on-study observation period, where the first and last ADA-positive samples (irrespective of any negative samples in between) are separated by a period less than 16 weeks, and the patient's last sampling time point is ADA negative.
- **A persistent ADA response** is defined by:
  - Treatment induced ADA detected at two or more sampling time points during the ADA on-study observation period, where the first and last ADA-positive on study samples are separated by at least 16 weeks (irrespective of any negative samples in between), OR
  - Treatment induced ADA detected in the last two sampling time points (both are positive), irrespective of the time period in between.
  - Indeterminate ADA is defined by treatment induced ADA detected only at the last sampling time point with all previous samples being negative

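### The two SAPs label the same short-span ADA pattern differently, both leave one pattern ending in a positive sample without a category, and the Phase 1 rules overlap for long spans

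*SAP*

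**What the plan says.** Phase 1 SAP 2.1.7 (Immune response) and Phase 2 SAP 2.1.6 (Immunogenicity) each sort treatment-induced ADA into three categories.

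- **Transient** (same in both): a single positive that is not the last sample; or two or more positives spanning less than 16 weeks, provided the patient's "last sampling time point is ADA negative".
- **Persistent**: both SAPs accept first and last positives "separated by at least 16 weeks (irrespective of any negative samples in between), OR". In the Phase 1 SAP nothing follows the final word. The Phase 2 SAP adds a second route: "Treatment induced ADA detected in the last two sampling time points (both are positive), irrespective of the time period in between".
- **Indeterminate**: the Phase 1 SAP has two routes, "Treatment induced ADA detected only at the last sampling time point with all previous samples being negative, OR" and then "The last two samples being ADA-positive and separated by a period of less than 16 weeks". The Phase 2 SAP has one: "Indeterminate ADA is defined by treatment induced ADA detected only at the last sampling time point with all previous samples being negative".

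Neither SAP says which category prevails if a patient meets two. Phase 1 SAP 2.4.6.3 and Phase 2 SAP 2.4.7 both plan the number and percentage of patients in each category, alongside the treatment-induced count, if at least one positive is seen.

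On sampling, Protocol 1.6 (footnote 25) says "To be performed on Day 1, Day 8, Day 15, Day 22 of Cycle 1 and Day 1 of cycle up to 10 cycles". Both SAPs say that "the ADA on-study observation period is defined as the time from first isatuximab administration until Cycle 10".

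**The concern.** Immunogenicity is part of a stated secondary objective in the protocol and in both SAPs, and these category counts are pre-specified. A programmer following each SAP literally meets three problems: opposite labels for the same results in the two parts, a double label in Phase 1, and a pattern with no label in either part. Patients in Phase 1 Cohort 2 and in Phase 2 may be on the same recommended dose, so a reader will naturally set the two tables side by side. Any difference in persistent ADA could then come from the definitions alone. Phase 2 SAP 2.4.7 also allows exploration of ADA impact on PK, safety and efficacy, and any version of that by persistence would need one settled definition.

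**Working it through.** The documents give no figure to reproduce. The check applies each rule set to possible result sequences.

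**Inputs.** The rules are those set out above, for patients without pre-existing ADA. The nominal on-study sampling times in weeks after first dose, from Protocol 1.6, are: Cycle 1 Days 8, 15 and 22 = weeks 1, 2, 3; Cycle N Day 1 = week 4 × (N − 1) for N = 2 to 10 = weeks 4, 8, …, 36. That is 3 + 9 = 12 samples.

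**Quantities.** Span = time of last positive minus time of first positive. Gap = time between the last two samples. On this schedule the gap is at most 4 weeks unless samples are missed, so the second Phase 1 indeterminate route applies to nearly every patient whose last two samples are positive.

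**Worked sequences**

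| Sample weeks | Results | Span (weeks) | Phase 1 SAP | Phase 2 SAP |
|---|---|---|---|---|
| 4, 8, 12 | − + + | 12 − 8 = 4 | indeterminate | persistent |
| 4, 8, 12 | + + + | 12 − 4 = 8 | indeterminate | persistent |
| 4, 8, 12 | + − + | 12 − 4 = 8 | none | none |
| 4, 8, 12 | + + − | 8 − 4 = 4 | transient | transient |
| 4, 8, 12 | − − + | 0 | indeterminate | indeterminate |
| 4 to 24, every 4 | all + | 24 − 4 = 20 | persistent and indeterminate | persistent |

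The third row fails each test in turn. It is not transient, because the last sample is positive. It is not persistent, because the span is under 16 weeks and the last two samples are not both positive. It is not indeterminate, because an earlier sample was positive and, again, the last two are not both positive.

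**All sequences with at least one positive, using the first n samples**

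| Phase 1 / Phase 2 label | n = 6 (to week 12) | n = 8 (to week 20) | n = 12 (to week 36) |
|---|---|---|---|
| transient / transient | 31 | 127 | 159 |
| indeterminate / indeterminate | 1 | 1 | 1 |
| indeterminate / persistent | 16 | 4 | 4 |
| none / none | 15 | 3 | 3 |
| persistent / persistent | 0 | 60 | 2908 |
| both persistent and indeterminate / persistent | 0 | 60 | 1020 |
| Total | 63 | 255 | 4095 |

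For every n from 1 to 12, the unclassified set is identical in the two SAPs: last sample positive, the one before it negative, an earlier positive, and span under 16 weeks.

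The failure to add up shows at n = 8. Phase 1 category counts sum to 127 transient + (1 + 4 + 60) indeterminate + (60 + 60) persistent = 312, against 255 sequences. Phase 2 counts sum to 127 + 1 + (4 + 60 + 60) = 252, which is 3 short.

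These are counts of possible sequences. They show which patterns are affected, not how often patients will have them.

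**The case against.** The strongest reply is that little depends on this breakdown. Protocol 13.4 and the Clinical Trial Summary have the parts analysed separately except for efficacy, and no pooled or comparative ADA table is specified. ADA-positive status, incidence and prevalence rest on pre-existing, induced or boosted ADA, not on these categories. Protocol 13.4.6 asks only for a summary by visit. The tables appear only if a positive is observed, sample-level listings let a reader reclassify, and Phase 1 expects just 6 to 12 evaluable patients. All of this stands, and it makes the point minor. It does not tell the programmer what to do with a patient who has two labels or none.

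Four stronger readings are tempting, and the documents do not support them.

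- *Every patient whose last two samples are positive changes category between parts.* With a span of 16 weeks or more the patient also meets the Phase 1 persistent rule. The fault there is a double label, not a switch.
- *A positive-negative-positive pattern within 16 weeks is never classified.* If a later, last sample is negative, both SAPs call it transient. Only sequences ending on the positive are left out.
- *The unfinished Phase 1 persistent list is itself an error.* A line may have been lost from the public copy. The conflict does not need it: if the missing line were the Phase 2 route, Phase 1 would give both labels to every patient with two closely spaced positives at the end.
- *It is wrong that Phase 1 patients with under 16 weeks of sampling cannot be persistent.* A duration-based definition cannot show persistence over short follow-up, so this is not a defect in itself.

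**Conclusion.** The point holds as a minor inconsistency in a planned secondary table. Three things are established from the text:

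1. With the last two samples positive and a span under 16 weeks, Phase 1 gives indeterminate and Phase 2 gives persistent.
2. With a span of at least 16 weeks and the last two positives less than 16 weeks apart, Phase 1 gives both persistent and indeterminate, with no precedence.
3. In both SAPs, an earlier positive followed by a negative second-to-last sample and a positive last sample, all within 16 weeks, has no category.

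The category counts are therefore not comparable between parts and need not sum to treatment-induced ADA. A reader might infer that the ADA rates or the efficacy result are in doubt; they are not, because neither uses these categories. The number of patients affected is probably small, but the documents give no ADA frequency from which to estimate it. The sequence counts assume the nominal schedule with no missed samples; the three conflicts follow from the rules and do not depend on it.

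**What to change.** Use one mutually exclusive and exhaustive set of definitions in both SAPs, applied in a stated order. One workable set for treatment-induced ADA is:

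1. Persistent, by the Phase 2 definition (span of at least 16 weeks, or last two samples both positive). This takes precedence.
2. Otherwise transient, if the last sample is negative.
3. Otherwise indeterminate. This covers a lone positive at the last sample and the pattern now left out.

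At n = 8 this gives 127 transient + (4 + 60 + 60) = 124 persistent + (1 + 3) = 4 indeterminate = 255, so the categories sum. Nothing in the documents makes the Phase 2 definition the only right choice. Another single set with stated precedence would serve equally well, provided both SAPs use it.

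The cost is a wording change in two SAPs and a rerun of the ADA category table. No new data are needed, since sample-level ADA results are already listed in both parts.
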